5.1 Baseline data collection study procedures

For ORCHID-BUD, we will contact the surrogate approximately 3-months (+/- 2 months) after hospital discharge in order to establish baseline cognition, PTSD, and depression. We will contact the surrogate listed on ORCHID by their preferred method of contact (phone, text message, or e-mail).

For the family member, we will administer the short form Informant Questionnaire on Cognitive Decline in the Elderly (IQCODE) establish the subject's baseline cognition; this 16-item questionnaire takes less than 5 minutes to complete. We will also ask the surrogate if they thought the patient was more confused than usual during hospitalization. We will also conduct the FAM-CAM and SQiD, which are informant-based delirium assessments, to further characterize delirium during hospitalization. We will ask them to estimate the number of days they felt the patient was confused. We will also ask if they (or any family members) were able to visit the patient in person, by phone, or by mobile device. We will also ask them to estimate the number of days the subject was hospitalized for and if applicable, duration of ICU length of stay and mechanical ventilation. We will also ask if the surrogate whether or not the subject has baseline dementia, PTSD, or depression. We will also ask about the subject's race, ethnicity, age, level of education, highest occupation, and region of residence. These data will be obtained over the phone, but the family member will have the option to complete the surveys via an online REDCap survey if preferred.

If no surrogate is listed for ORCHID, we will contact the patient by their preferred method of contact (phone, text message, or e-mail). If the surrogate is available, we obtain the surrogate's contact information. For the patient, we will administer the IQCODE and ask if they have baseline dementia, PTSD, or depression. We will also ask if they were on cholinesterase inhibitors before they were hospitalized for COVID-19. We will also ask their race, ethnicity, age, level of education, highest occupation, and region of residence. We will ask patients some questions about their hospitalization. We will also ask how long they were hospitalized, how long were they in the ICU, and how long they were mechanically ventilated. These questions may be answered by their family member or caregiver if requested. We will also ask patients if they felt confused, disoriented, or had hallucinations during hospitalization. We will ask them to estimate the number of days during the hospitalization they felt they had these symptoms. We will also ask how much contact family and friends had with the patient during hospitalization and if the contact was in person, by video conferencing, or by phone. We will also ask about the subject's race, ethnicity, age, level of education, highest occupation, and region of residence. These data will be obtained over the phone, but the subject will have the option to complete the surveys via an online REDCap survey if preferred.

After the conversation has concluded, we will let them know that we will contact them approximately 12-months (+/- 3 months) after randomization to assess their cognition and psychological well-being using a phone battery. We will also let them know that we will give them a gift card after they complete the 12-month phone call.

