6.3.2 Long-term Follow-up

We will follow-up selected patients at 3, 6, and 12 months to assess vital status, cognition, basic and instrumental activities of daily living, quality of life, employment status, physical disability, and psychological distress (i.e., depression, post-traumatic stress disorder, etc.), place of residence, and rehospitalizations. These assessments may occur by phone, in-person, or videoconferencing.

Follow-up procedures in ORCHID are further specified by the Outcomes Related to COVID-19 treated with Hydroxychloroquine among In-patients with symptomatic Disease – Brain Outcomes and Psychological Distress (ORCHID-BUD) ancillary study. In summary, ORCHID-BUD will perform a phone battery at 12-months to determine cognition, post-traumatic stress disorder, and depression. In order to determine incident cases of cognitive impairment, post-traumatic stress disorder, and depression, baseline data will be collected from the subject’s family member or friend or the subject him/herself. Details of ORCHID-BUD study procedures are described in **Appendix E**.

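### When no surrogate is listed, ORCHID-BUD gives an informant questionnaire (IQCODE) to the patient, even if that call identifies an informant who could answer it

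*Protocol*

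**What the plan says.** Protocol section 6.3.2 states why a baseline is needed: "In order to determine incident cases of cognitive impairment, post-traumatic stress disorder, and depression, baseline data will be collected". It allows the source to be a relative, a friend or the patient.

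Appendix E, section 5.1, gives the procedure. The surrogate is the default contact, "approximately 3-months (+/- 2 months) after hospital discharge in order to establish baseline cognition, PTSD, and depression". For that route the text reads: "For the family member, we will administer the short form Informant Questionnaire on Cognitive Decline in the Elderly (IQCODE"). The family member also receives two further informant-based tools, the FAM-CAM and the SQiD, which concern delirium.

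If the parent trial lists no surrogate, the patient is contacted instead. Two sentences then stand next to each other. The first is "If the surrogate is available, we obtain the surrogate's contact information". The second is "For the patient, we will administer the IQCODE and ask if they have baseline dementia, PTSD, or depression". Later in the same paragraph, after the questions on length of hospital stay, ICU stay and ventilation, comes "These questions may be answered by their family member or caregiver if requested".

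**The concern.** Section 5.1 names the IQCODE as an informant instrument and then uses it as a self-report instrument, without naming a self-report version or giving a reason. The patient answers after COVID-19, and new problems with memory or insight are exactly what the study is looking for. Such a patient may misjudge his or her own earlier state in either direction. Old impairment could then be counted as new, or new impairment as old.

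Informant-rated and self-rated baselines would also stand side by side although different kinds of respondent produced them. What is at stake is how cleanly ORCHID-BUD can separate incident from pre-existing cognitive impairment.

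**Working it through.** The point concerns measurement, so the main check is a comparison of the texts.

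1. **Which tools cross over.** The surrogate route in 5.1 has three informant tools: IQCODE, FAM-CAM and SQiD. The patient route drops the FAM-CAM and SQiD and asks the patient directly about confusion, disorientation and hallucinations. The IQCODE alone is carried across unchanged.

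2. **Whether the patient's IQCODE is conditional.** The trigger is that no surrogate is listed, not that no informant can be reached. Contact details are taken if a surrogate is available, but no sentence says that this person then completes the IQCODE or that their answers replace the patient's.

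3. **Whether "These questions may be answered by their family member or caregiver if requested" covers the IQCODE.** It follows the questions on hospitalization, ICU stay and ventilation, and it applies only on request. It does not redirect the IQCODE.

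4. **When the rating is made.** The window of 3 months plus or minus 2 runs from 3 − 2 = 1 to 3 + 2 = 5 months after discharge. Appendix E 5.2 lets missed baseline items be collected at the 12-month call, which has a window of plus or minus 3 months. A self-rated baseline could therefore be taken on the same call as the outcome.

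5. **What the baseline is for.** Section 6.3.2 ties baseline data to incident cases. No section gives an IQCODE cutoff or a rule that turns the score into an incident case.

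6. **Size.** Appendix E section 12 gives 460 enrolled, 70% surviving, 93% of those eligible and 90% of those completing the battery: 460 × 0.70 × 0.93 × 0.90 = 269.5, which reproduces the stated 270. The share with no listed surrogate is not given. Under assumed shares:

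| Assumed share | Patients out of 270 |
|---|---|
| 5% | 13.5 |
| 10% | 27 |
| 20% | 54 |
| 30% | 81 |
| 50% | 135 |

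Each count is a ceiling for its share, because in practice some of these patients may supply an informant who answers.

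**The case against.** The best defence is that the fallback is deliberate and minor. Section 6.3.2 openly allows the patient as a source, the surrogate is the default, and taking a surrogate's contact details just before the IQCODE sentence suggests an intention to call that person. The IQCODE is also not the only baseline information. Dementia is recorded as a comorbidity at enrollment (6.1), the patient is asked directly about dementia and cholinesterase inhibitors, and patients who were non-verbal or unable to follow simple commands before COVID-19 are excluded. Most of this stands and limits the point. It does not close it: the intention to call the surrogate is not written down, and the exclusion leaves milder prior impairment in the cohort.

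A reader might infer more than the documents support:

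- **That the primary endpoint or the hydroxychloroquine comparison is compromised.** The endpoint is the patient's own 12-month battery, and with blinded randomized arms there is no reason to expect respondent type to differ by arm.
- **That self-rated scores could never be told apart.** The two routes carry different items, so the respondent could usually be worked out. The SAP (Appendix B) leaves ORCHID-BUD to separate reporting, so the lack of a rule here does not show that none was planned.
- **That respondent type tracks severity.** Sections 10.2 and 10.6 make this plausible, but nothing says that a surrogate is listed only when a representative gave consent.
- **That only informant ratings should be used in the main analysis.** This would drop patients without informants, who may differ from the rest, and so trade measurement error for selection. Falling back on the direct dementia question would still rely on the same patient.

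**Conclusion.** The point holds as a modest improvement to an ancillary study. As written, Appendix E 5.1 has the patient complete an informant questionnaire whenever no surrogate is listed, including when the call itself identifies one. Some retrospective baselines would be self-rated after the illness and not comparable with informant-rated ones.

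The number affected is unknown, and the counts above rest wholly on assumed shares. The effect on classification cannot be sized either, because the documents give no rule for incident cases and no figure for how a self-completed IQCODE performs. The conclusion assumes that the IQCODE contributes to identifying incident impairment, as section 6.3.2 implies for baseline data generally.

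**What to change.** In Appendix E 5.1, state that when the patient call identifies a surrogate, the IQCODE is administered to that informant, and that the patient completes it only if no informant can be reached. Record who answered. Repeat the incident-impairment analysis restricted to informant-rated baselines as a sensitivity analysis, and read it alongside the dementia comorbidity from enrollment (6.1), which does not depend on the follow-up respondent.

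The cost is a wording change, one data field and one extra informant contact for some patients; section 5.1 puts the questionnaire at under 5 minutes. The sensitivity analysis will have a smaller sample and may be selective, which is why it should accompany the main analysis and not replace it.

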5.2 Twelve-month study procedures

The CIBS Center will then contact enroll subjects at approximately 12-months (+/- 3 months). We will perform the phone battery as described in the **Primary Endpoints (Section 10) and Secondary Endpoints (Section 11)** section. Any data not obtained during the baseline phone call will be obtained during the 12-month phone call to minimize missing data. After the 12-month follow-up is completed, patients will be given a gift card.

It is possible that ORCHID-BUD patients will be co-enrolled with other PETAL network COVID-19 trials (e.g., BLUE CORAL) who are conducting long-term follow-ups. We may coordinate with the University of Washington and University of Michigan study teams to streamline data collection and minimize overburdening the patient.

5.3 Medical Record Review

We will use electronic medical records, in whatever institutions make this this available, to obtain detailed data regarding these potentially modifiable risk factors. Specifically, we will evaluate how modifiable risk factors such as the use of sedative medications and oxygen therapy, mechanical ventilation settings, social isolation, ventilator weaning protocols, intravenous fluid administration, antibiotics, medications such as ACE-inhibitors, ARBs, antacids, and pressors affect the 12-month outcomes.

6. Risks: Because ORCHID-BUD is only adding a comprehensive phone battery at 12-months, its risks are minimal:
 - 6.1 Fatigue or distress: For ORCHID-BUD specifically, subjects will undergo a comprehensive phone battery at 12-months that can take up to 45 to 60 minutes to perform. There is a small risk that the patient may become fatigued or distressed during the study's cognitive assessments.
 - 6.2 Confidentiality: Because patient identifiers are accessed throughout all phases of the study, there is a small risk of loss of patient confidentiality.
7. Inclusion Criteria: All patients enrolled in ORCHID will be included.
8. Exclusion Criteria: ORCHID-BUD will exclude patients who are:
 - (1) non-English or non-Spanish speaking,
 - (2) deaf, or
 - (3) non-verbal or unable to follow simple commands prior to the COVID-19 illness.

We will exclude non-English and Non-Spanish speaking patients because our neuropsychological raters can only provide their assessments in these languages. We will also exclude patients who are non-verbal or unable to follow simple commands prior to the COVID-19 illness to exclude patients with end-stage dementia.

9. Randomization and Study Initiation Time Window: The ORCHID-BUD ancillary study will enroll patients from ORCHID parent study. ORCHID-BUD study activities will the subject and/or surrogates approximately one to three months after ORCHID randomization. At approximately 12-months (+/- 3 months) after randomization, we will call the patients and conduct the phone battery to assess cognition, PTSD, and depression.

10. Primary Endpoint

	Assessment	Domain	Description
Cognition	Telephone Montreal Cognitive Assessment	Global Cognition	Measure of global cognition and assesses attention concentration, memory, language, conceptual thinking, calculations, and orientation.
	WAIS-IV Digit Span ³	Attention	Subject repeats a string of numbers forwards, backwards, and ascending order
	Hayling test ⁴	Executive Function	It consists of two sets of 15 sentences; the examiner reads the questions aloud and subject completes the sentences
	DKEFS Verbal Fluency ⁵	Language	Subject is asked to name as many animals they can think of 60 seconds and as many words that begin with the letter “F”, “A”, and “S” over 60 seconds
	Paragraph Recall - Immediate ⁶	Immediate Memory	Subject is read a paragraph and then recalls the paragraph immediately
	Paragraph Recall - Delayed ⁶	Delayed Memory	Subject recalls the paragraph memorized from the immediate memory task 15 to 20 minutes later
	WAIS-IV Similarities ³	Reasoning/Verbal Abstraction	Subject is given two words and then is asked how they are alike
	DKEFS Proverbs ⁵	Reasoning/Verbal Abstraction	Subject is asked to interpret 5 proverbs
Psychological	Hospital Anxiety and Depression Scale ⁷	Depression	Multiple-choice inventory that is used for measuring the severity of depression
	PTSD Checklist for the DSM-V (PCL-5) ⁸	PTSD	Multiple-choice questions reflecting DSM-IV symptoms of PTSD. Subjects with a score of > 35 will receive a formal assessment performed over the phone by a clinical psychologist using the CAPS-5

Table 1. Telephone Battery to assess cognitive, psychological, and functional outcomes. WAIS-IV, Wechsler Adult Intelligence Scale-IV; DKEFS, Delis–Kaplan Executive Function System; PTSD, Post-Traumatic Stress Disorder; Clinician Administered PTSD Scale for the DSM-5 (CAPS-5).

11. Secondary Endpoint: We will also record 12-month mortality and place of residence. We will also ask the number of times the patient was re-hospitalized since the index hospitalization.

12. Sample Size / Interim Monitoring

All patients enrolled in the ORCHID parent study will be screened for ORCHID-BUD. ORCHID will enroll 460 patients who are hospitalized with COVID-19. We estimate that 70% will survive and of these, 93% will meet ORCHID-BUD’s eligibility criteria. We estimate that we will

successfully complete the phone battery in 90% of eligible patients providing 270 patients for ORCHID-BUD's analysis.

1. INTRODUCTION

This document is the Statistical Analysis Plan for the ORCHID Trial and accompanies version 4 of the ORCHID protocol (dated June 4, 2020). The main text of this document describes the statistical approaches and methods used for the trial. Appendix A is a list of outcome variables along with their definitions and methods for analysis. Appendix B includes definitions for derived and composite variables and imputation methods. Appendix C contains a list of on-study measurements, their definitions, and methods for analysis.

2. BRIEF TRIAL SUMMARY

Title	Hydroxychloroquine for the Early Treatment of COVID-19 in Hospitalized Adults: A Multicenter Randomized Clinical Trial
Acronym	ORCHID O utcomes R elated to C COVID-19 treated with H ydroxychloroquine among I n-patients with symptomatic D isease
Background	Hydroxychloroquine is an antimicrobial agent with immunomodulatory and antiviral properties that has demonstrated in vitro activity against SARS-CoV-2, the virus that causes COVID-19. Preliminary reports suggest potential efficacy in small human studies. Clinical trial data are needed to determine whether hydroxychloroquine is effective in treating COVID-19.
Study Design	Blinded, multicenter, placebo-controlled randomized clinical trial
Intervention group	Hydroxychloroquine 400 mg twice daily for two doses, then 200 mg twice daily for the subsequent eight doses (10 total doses)
Control group	Matched placebo twice daily for 10 total doses
Sample Size	Up to 510 patients
Population	Hospitalized adults with acute respiratory illness from laboratory-confirmed SARS-CoV-2 infection.
Randomization	Eligible participants will be randomized 1:1 to hydroxychloroquine versus placebo. Randomization will be completed in permuted blocks of variable size and stratified by site.
Blinding	Patients, treating clinicians, trial personnel, and outcome assessors will be blinded to group assignment.
Primary Outcome	COVID Ordinal Outcomes Scale on Study Day 15: 
1. Death2. Hospitalized on invasive mechanical ventilation or ECMO3. Hospitalized on non-invasive ventilation or high flow nasal cannula4. Hospitalized on supplemental oxygen5. Hospitalized not on supplemental oxygen6. Not hospitalized with limitation in activity7. Not hospitalized without limitation in activity
Analysis	The primary analysis will be an intention-to-treat comparison of the primary outcome between patients randomized to hydroxychloroquine versus placebo using a proportional odds model.

3. TRIAL DESCRIPTION

3.1 Background

Coronavirus Disease 2019 (COVID-19) is an acute respiratory infectious illness caused by *severe acute respiratory syndrome coronavirus 2* (SARS-CoV-2).^{1,2} Based on mechanism of action and early clinical experiences, several agents currently available in the United States (US) have been proposed as potential therapies to prevent progression of COVID-19.³⁻⁵ Among these potential therapies, hydroxychloroquine has generated substantial interest due to its antiviral and immunomodulatory activity and established safety profile. Many US hospitals have recommended hydroxychloroquine as first-line therapy for hospitalized patients with COVID-19. Thus, data on the safety and effectiveness of hydroxychloroquine for the treatment of COVID-19 are urgently needed to inform practice. The ORCHID trial was designed to evaluate the safety and efficacy of hydroxychloroquine for hospitalized adults with COVID-19.

3.2 Study Aims

3.2.1 Study aim

To compare the effect of hydroxychloroquine versus placebo on clinical status 14 days after randomization (Study Day 15) as assessed with a seven-category ordinal scale, among hospitalized adults with COVID-19.

3.2.2 Study hypothesis

Among adults hospitalized with COVID-19, administration of hydroxychloroquine will improve clinical status 14 days after randomization.

3.3 Study Design

ORCHID is an investigator-initiated, multicenter, blinded, placebo-controlled, randomized clinical trial evaluating hydroxychloroquine for the treatment of hospitalized adults with COVID-19.

4. STUDY POPULATION

4.1 Inclusion Criteria

1. Age ≥ 18 years
2. Currently hospitalized or in an emergency department with anticipated hospitalization.
3. Symptoms of acute respiratory infection, defined as one or more of the following:
 - a. Cough
 - b. fever ($> 37.5^{\circ} \text{C} / 99.5^{\circ} \text{F}$)
 - c. shortness of breath (operationalized as any of the following: subjective shortness of breath reported by patient or surrogate; tachypnea with respiratory rate ≥ 22 /minute; hypoxemia, defined as $\text{SpO}_2 < 92\%$ on room air, new receipt of supplemental oxygen to maintain $\text{SpO}_2 \geq 92\%$, or increased supplemental oxygen to maintain $\text{SpO}_2 \geq 92\%$ for a patient on chronic oxygen therapy).
 - d. sore throat
4. Laboratory-confirmed SARS-CoV-2 infection within the past 10 days prior to randomization

4.2 Exclusion Criteria

1. Prisoner
2. Pregnancy
3. Breast feeding
4. Unable to randomize within 10 days after onset of acute respiratory infection symptoms
5. Unable to randomize within 48 hours after hospital arrival
6. Seizure disorder
7. Porphyria cutanea tarda
8. QTc >500 ms on electrocardiogram within 72 hours prior to enrollment
9. Diagnosis of Long QT syndrome
10. Known allergy to hydroxychloroquine, chloroquine, or amodiaquine
11. Receipt in the 12 hours prior to enrollment, or planned administration during the 5-day study period that treating clinicians feel cannot be substituted for another medication, of any of the following: amiodarone; cimetidine; dofetilide; phenobarbital; phenytoin; sotalol
12. Receipt of >1 dose of hydroxychloroquine or chloroquine in the 10 days prior to enrollment
13. Inability to receive enteral medications
14. Refusal or inability to be contacted on Day 15 for clinical outcome assessment if discharged prior to Day 15
15. Previous enrollment in this trial
16. The treating clinical team does not believe equipoise exists regarding the use of hydroxychloroquine for the treatment of this patient

4.3 Sample Size and Interim Analyses

The anticipated enrollment for the trial is 510 patients. We calculated the sample size under the assumption that we would have an interim analysis after approximately every 102 patients. The interim analyses employ a Bayesian framework evaluating the primary outcome (Day 15 COVID Ordinal Outcomes Scale, described below). An odds ratio >1.0 indicates more favorable clinical status in the hydroxychloroquine group than the placebo group. The stopping criteria proposed to (and approved by) the data and safety monitoring board include:

- If we determine there is >95% probability of the odds ratio being >1.0, the DSMB should consider stopping the trial for efficacy.
- If we determine there is >90% probability that the odds ratio is <1.1, the DSMB should consider stopping the trial for futility or harm.
- If we determine there is >70% probability that the odds ratio is <0.70, the DSMB should consider stopping the trial for significant harm.

We will use a prior odds ratio of 1.0 (equal chance of harm and benefit; mean log OR of 0.0) and a prior distribution of the standard error for its log set at 0.352 for tests of efficacy and a non-informative prior for tests of futility and harm.

